2.8.2 Laboratory data

The summary of lab data will only include treatment emergent data, which are defined as those lab assessments after the first dose of study treatment and on or before last dose + 84 days.

Reported laboratory assessments with either a less than or greater than sign ("<" or ">") will be used for analysis after removal of the sign and conversion to standard unit. These laboratory data will be displayed in listings using the standard unit with the reported sign ("<" or ">").

The summary of laboratory evaluations will be presented for three groups of laboratory tests (hematology, chemistry and urinalysis). In addition to the individual laboratory parameters the

Novartis	Confidential	Page 19 of 45
SAP		Study No. CAIN457P12301

ratios "total cholesterol / HDL" and "apolipoprotein B / apolipoprotein A1" will be derived and summarized.

For urinalysis, frequency tables will be presented.

Descriptive summary statistics for the change from baseline to each study visit will be presented. These descriptive summaries will be presented by laboratory test and treatment group. Change from baseline will only be summarized for subjects with both baseline and post baseline values and will be calculated as:

change from baseline = post baseline value – baseline value

For each parameter, the maximum change (maximum decrease and maximum increase) from baseline, if appropriate for each study phase, will be analyzed analogously.

In addition, shift tables will be provided for all parameters to compare a subject's baseline laboratory evaluation relative to the visit's observed value. For the shift tables, the normal laboratory ranges will be used to evaluate whether a particular laboratory test value was normal, low, or high for each visit value relative to whether or not the baseline value was normal, low, or high. If appropriate, the shifts to the most extreme laboratory test value within a treatment phase (either initial or entire) will be presented as well (including category "high and low"). These summaries will be presented by laboratory test and treatment group.

The following laboratory parameters will be analyzed with respect to numerical Common Terminology Criteria for Adverse Events (CTCAE) grades, given in Table 2-2: hemoglobin, platelets, white blood cell count, neutrophils, lymphocytes, creatinine, total bilirubin (TBL), gamma-glutamyl transferase (GGT), alanine aminotransferase (ALT), aspartate aminotransferase (AST), alkaline phosphatase (ALP), glucose, cholesterol, triglycerides (TG).

These summaries will be split into hematology and chemistry for study level reports and the pooled summary of clinical safety.

CTCAE v4.03 Term	Grade 1	Grade 2	Grade 3	Grade 4
HGB decreased				
(Anemia)	<lln 100="" g="" l<="" td="" –=""><100 – 80 g/L	<80 g/L	See note below	</lln>	<100 – 80 g/L	<80 g/L	See note below
Platelet count				
decreased	<lln 10e9="" 75.0="" l<="" td="" ×="" –=""><75.0 - 50.0 × 10e9 /L	<50.0 – 25.0 × 10e9 /L	<25.0 × 10e9 /L	</lln>	<75.0 - 50.0 × 10e9 /L	<50.0 – 25.0 × 10e9 /L	<25.0 × 10e9 /L
White blood cell				
decreased	<lln -="" 10e9="" 3.0="" l<="" td="" ×=""><3.0 - 2.0 × 10e9 /L	<2.0 - 1.0 × 10e9 /L	<1.0 × 10e9 /L	</lln>	<3.0 - 2.0 × 10e9 /L	<2.0 - 1.0 × 10e9 /L	<1.0 × 10e9 /L
Neutrophil count				
decreased	<lln -="" 1.5="" 10e9="" l<="" td="" ×=""><1.5 - 1.0 × 10e9 /L	<1.0 - 0.5 × 10e9 /L	<0.5 × 10e9 /L	</lln>	<1.5 - 1.0 × 10e9 /L	<1.0 - 0.5 × 10e9 /L	<0.5 × 10e9 /L
Lymphocyte count				
decreased	<lln -="" 0.8="" 10e9="" l<="" td="" ×=""><0.8 - 0.5 × 10e9 /L	<0.5 - 0.2 × 10e9 /L	<0.2 × 10e9 /L	</lln>	<0.8 - 0.5 × 10e9 /L	<0.5 - 0.2 × 10e9 /L	<0.2 × 10e9 /L
Creatinine increased*	>1 - 1 5 x haseline [.]	>1.5 - 3.0 ×	>3.0 haseline	
	$> N = 1.5 \times N$	Daseline; >1.5 - 3.0 X	$>3.0 - 6.0 \times 111 \text{ N}$	>6.0 x 1 N
TRI increased	$> U N = 1.5 \times U N$	>15-30×111N	>3.0 - 10.0 × UI N	>10.0 × 111 N
GGT increased	$> U N = 2.5 \times U N$	>25-50 × ULN	>5.0 - 20.0 × ULN	>20.0 × 111 N
ALT increased		>3.0 - 5.0 × ULN	>5.0 - 20.0 × ULN	>20.0 × ULN
AST increased		>3.0 - 5.0 × ULN	>5.0 - 20.0 × ULN	
		>3.0 - 5.0 × ULN	>5.0 - 20.0 × ULN	>20.0 × ULN
	20LIN - 2.3 × ULIN	~2.5 - 5.0 × ULN	~5.0 - 20.0 × ULN	~20.0 ^ ULN
(Hyperglycemia)	>ULN - 8.9 mmol/L	>8.9 - 13.9 mmol/L	>13.9 - 27.8 mmol/L	>27.8 mmol/L

 Table 2-2
 CTCAE grades for laboratory parameters to be analyzed

Novartis	Confidential	Page 20 of 45
SAP		Study No. CAIN457P12301

CTCAE v4.03 Term	Grade 1	Grade 2	Grade 3	Grade 4
Glucose decreased				
(Hypoglycemia)	<lln -="" 3.0="" l<="" mmol="" td=""><3.0 - 2.2 mmol/L	<2.2 - 1.7 mmol/L	<1.7 mmol/L	</lln>	<3.0 - 2.2 mmol/L	<2.2 - 1.7 mmol/L	<1.7 mmol/L
Cholesterol high	>ULN - 7.75 mmol/L	>7.75 - 10.34 mmol/L	>10.34 - 12.92 mmol/L	>12.92 mmol/L
Hypertriglyceridemia	1.71 - 3.42 mmol/L	>3.42 - 5.7mmol/L	>5.7 - 11.4 mmol/L	>11.4 mmol/L

Note: Grade 4 Hemoglobin events are defined as life-threatening anemia events and will not be displayed in the table, as a numerical range is not provided in the CTCAE.

*Note: for "creatinine increased" the baseline criteria do not apply.

Shift tables will be presented comparing baseline laboratory result (CTCAE grade) with the worst results (expressed in CTCAE grade) during the treatment phase (either initial or entire) analyzed. Of note, baseline will be defined as last assessment prior to first dosing in initial treatment phase. Subjects with abnormal laboratory values will be listed and values outside the normal ranges will be flagged.

Summaries for newly occurring or worsening clinically notable lipid abnormalities will also be provided cumulatively for each of the following parameters and categories:

- HDL:
 - <=LLN
 - $\bullet \quad <\!\!0.8 \times LLN$
- LDL, cholesterol, triglycerides:
 - >=ULN
 - >1.5 × ULN
 - >2.5 × ULN

Newly occurring or worsening liver enzyme abnormalities will also be summarized based on the event criteria given in Table 2-3:

1	Novartis
S	SAP

Parameter	Criterion
ALT	>3×ULN; >5×ULN; >8×ULN;>10×ULN, >20×ULN
AST	>3×ULN; >5×ULN; >8×ULN >10×ULN; >20×ULN
ALT or AST	>3×ULN; >5×ULN; >8×ULN >10×ULN; >20×ULN
TBL	>1.5×ULN, >2×ULN, >3×ULN,
ALP	>2×ULN, >3×ULN. >5×ULN
ALT or AST &	ALT or AST>3×ULN & TBL >2×ULN;
TBL	ALT or AST >5×ULN & TBL >2×ULN;
	ALT or AST >8×ULN & TBL >2×ULN;
	ALT or AST >10×ULN & TBL >2×ULN
ALP & TBL	ALP >3×ULN & TBL >2×ULN
	ALP >5×ULN & TBL >2×ULN
ALT or AST &	ALT or AST>3×ULN & TBL >2×ULN & ALP <2×ULN (Hy's Law)
TBL & ALP	Note: elevated ALP may suggest obstruction as a consequence of gall bladder or
	bile duct disease; ALP may also be increased in malignancy. FDA therefore terms
	that cases of ALT or AST >3xLILN & TBL >2xLILN & ALP >2xLILN may not result
	in severe DILI.
Nataa	

Notes:

In studies which enroll subjects with pre-existing liver disease, baseline LFT may be increased above ULN; in such a case it is meaningful to add the condition "and worse than baseline" to the abnormality criteria

For a combined criterion to be fulfilled, all conditions have to be fulfilled on the same visit. The criteria are not mutually exclusive, e.g., a subject with $ALT = 6.42 \times ULN$ is counted for $ALT > 3 \times ULN$ and $ALT > 5 \times ULN$.

Individual subject data listings will be provided for subjects with abnormal laboratory data. Data of subjects with newly occurring or worsening liver enzyme abnormalities will be listed in an additional listing.

Boxplots over time will be presented for selected laboratory parameters (neutrophils, liver and lipid parameters).

Individual subject data listing will be provided for hematology.

2.8.3 Other safety data

2.8.3.1 Vital signs

The summary of vital signs will only include treatment emergent data, which are defined as those vital sign measurements after the first dose of study treatment and on or before last dose + 84 days.

Analysis in vital sign measurement using descriptive summary statistics for the change from baseline for each post-baseline visit will be performed. These descriptive summaries will be presented by vital sign and treatment group. Change from baseline will only be summarized for subjects with both baseline and post-baseline values and will be calculated as:

Novartis	Confidential	Page 22 of 45
SAP		Study No. CAIN457P12301

change from baseline = post-baseline value – baseline value

The number and percentage of subjects with newly occurring notable vital signs will be presented. Criteria for notable vital sign abnormalities are provided in Table 2-4:

 Table 2-4
 Criteria for notable vital sign abnormalities

Vital sign (unit)	Notable abnormalities	
Systolic blood pressure (mmHg)	>= 140 mmHg or < 90 mmHg	
Diastolic blood pressure (mmHg)	>=90 mmHg or <60 mmHg	
Pulse (bpm)	> 100 bpm or <60 bpm	

2.8.3.3 Compour	nd specific	safety eval	uation
-----------------	-------------	-------------	--------

Safety topics of interest, such as risks defined in the Risk Management Plan (RMP) or topics of interest regarding signal detection or routine analysis are defined in the Program Case Retrieval Sheet that is stored in CREDI at the path Cabinets/CREDI Projects/A/AIN457A/Integrated Medical Safety.

The crude incidence and exposure-adjusted incidence rates for RMP risks will be summarized. In addition, listings will be provided presenting which subjects experienced which risk.

Important note: For the evaluation of RMP risks primary and secondary system organ classes of the MedDRA dictionary will be considered.

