10. Past medical history of infection with HIV or hepatitis B prior to randomization or active infection or on treatment for Hepatitis C at randomization

11. History of lymphoproliferative disease or any known malignancy, or history of malignancy of any organ system treated or untreated within the past 5 years, regardless of whether there is evidence of local recurrence or metastases (except for skin Bowen's disease, or basal cell carcinoma or actinic keratoses that have been treated with no evidence of recurrence in the past 12 weeks; carcinoma in situ of the cervix or non-invasive malignant colon polyps that have been removed)
12. Use or planned use of prohibited concomitant medication (see [Section 6.2.2](#))
13. Inability or unwillingness to undergo repeated venipuncture (e.g., because of poor tolerability or lack of access to veins)
14. Pregnant or nursing (lactating) women, where pregnancy is defined as the state of a female after conception and until the termination of gestation, confirmed by a positive hCG laboratory test
15. History or evidence of ongoing alcohol or drug abuse, within the last six months before randomization
16. Screening total WBC count <3,000/ μ l, or platelets <100,000/ μ l or neutrophils <1,500/ μ l or hemoglobin <8.5 g/dl (85 g/L)
17. History of clinically significant liver disease or liver injury indicated by abnormal liver function tests, such as SGOT (AST), SGPT (ALT), alkaline phosphatase and serum bilirubin. The investigator should be guided by the following criteria:
 - Any single parameter may not exceed 2 x the upper limit of normal (ULN). A single parameter elevated up to and including 2 x ULN should be re-checked once more as soon as possible, and in all cases, at least prior to randomization, to rule-out laboratory error.
 - If the total bilirubin concentration is increased above 2 x ULN, total bilirubin should be differentiated into the direct and indirect reacting bilirubin. In any case, serum bilirubin should not exceed the value of 1.6 mg/dL (27 μ mol/L)
18. Significant medical problems or diseases, including but not limited to the following: uncontrolled hypertension (\geq 160/95 mmHg), congestive heart failure (New York Heart Association status of class III or IV), uncontrolled diabetes, or very poor functional status precluding ability to perform self-care
19. Plans for administration of live vaccines during the study period or within 6 weeks prior to randomization

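### The notable vital-sign count in SAP 2.8.3.1 misses a further rise in a blood-pressure parameter that is already above its limit at baseline

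*SAP*

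**What the plan says.** **Counting rule.** SAP 2.8.3.1: "The number and percentage of subjects with newly occurring notable vital signs will be presented". The SAP does not define newly occurring for vital signs.

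**Limits.** SAP Table 2-4 has a separate row for each parameter, with one high and one low limit. Systolic pressure: ">= 140 mmHg or < 90 mmHg". Diastolic pressure: ">=90 mmHg or <60 mmHg". There is no higher tier and no change-from-baseline criterion.

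**Entry ceiling.** Protocol 5.2, exclusion 18, names uncontrolled hypertension with a ceiling given as "160/95 mmHg), congestive heart failure". It does not say whether both components must be reached or only one.

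**Laboratory rules in the same SAP.** For lipids, 2.8.2 says: "Summaries for newly occurring or worsening clinically notable lipid abnormalities will also be provided cumulatively". For liver tests: "Newly occurring or worsening liver enzyme abnormalities will also be summarized based on the event criteria". Both use several thresholds. Laboratory data also get shift tables from baseline to the worst value. No shift table is planned for vital signs.

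**Other vital-sign output.** SAP 2.8.3.1 also states: "Analysis in vital sign measurement using descriptive summary statistics for the change from baseline for each post-baseline visit will be performed". SAP 2.1 includes the maximum among the summary statistics, and SAP 5.3 says that all collected data are listed.

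**The concern.** A count of new occurrences against a single limit works when nearly everyone starts below the limit. Here the eligibility criteria let subjects start above it. For such a subject the count is silent on the question a safety reader would ask: did this already raised pressure go up further on treatment?

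The rule also ranks changes oddly. A crossing of 2 mmHg is an event, while a rise of 40 mmHg from just above the limit is not. Vital signs are named in the trial's safety objective, and this table is the planned count, by arm, of subjects with abnormal measured values.

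**Working it through.** The plan states no figure for this count, so there is nothing to reproduce. The check has three parts.

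**1. Who can enter already notable.** Table 2-4 sets the high limits at 140 and 90; exclusion 18 sets the ceiling at 160/95. If either component at its ceiling excludes, the admissible values that are already notable are systolic 140–159 and diastolic 90–94. If both must be reached, the admissible range is wider. The two bands are therefore the narrower case.

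**2. What is counted.** Newly occurring is read as below the high limit at baseline and at or above it after the first dose, separately for each parameter. The pairs below are illustrative, and every baseline is admissible under either reading of the ceiling.

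| Baseline → later | Change (sys/dia) | New systolic event | New diastolic event |
|---|---|---|---|
| 145/85 → 185/88 | +40/+3 | no | no |
| 159/94 → 200/120 | +41/+26 | no | no |
| 145/85 → 185/105 | +40/+20 | no | yes |
| 130/92 → 175/110 | +45/+18 | yes | no |
| 138/85 → 140/85 | +2/0 | yes | no |

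Rows 1 and 2 show the gap. Rows 3 and 4 show its limit: a subject high on one parameter can still register on the other. Only a subject high on both is fully blocked for rises.

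**3. Effect on the percentage.** Let *q* be the share of an arm already notable for a parameter, and *r* the incidence among the rest. If everyone stays in the denominator of 250 planned per arm:

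reported incidence = 250 × (1 − *q*) × *r* / 250 = (1 − *q*) × *r*

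The documents do not give *q*, so 5–30% is an assumed range. *r* = 10% is only an example.

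| *q* | Subjects per arm not at risk (250 × *q*) | Reported when *r* = 10% | Factor (1 − *q*) |
|---|---|---|---|
| 5% | 12.5 | 9.5% | 0.95 |
| 10% | 25 | 9% | 0.90 |
| 20% | 50 | 8% | 0.80 |
| 30% | 75 | 7% | 0.70 |

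The factor applies only if subjects notable at baseline stay in the denominator. The text does not settle this: SAP 5.4.3.1 describes *n* both as subjects at risk of the event and as the total number of subjects.

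**The case against.** The strongest objection is that large rises are not lost from the report. Change from baseline is summarised at each visit for every subject with both values, whatever the baseline, and the maximum is shown. All data are listed. Adverse events are tabulated too, and SAP 2.8.1 includes events that predate dosing and then become more severe. This stands in part. But a maximum shows one extreme per arm and visit, listings give no rate, and an adverse event depends on the investigator's judgement (Protocol 10.1.1 sets conditions before an abnormal test result becomes one). None of these gives the number of subjects per arm whose measured values worsened.

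Two further objections limit the weight of the point, and both stand. The output is descriptive, and Protocol 12.5.2 promises only change-from-baseline summaries for vital signs. Randomisation is 1:1, so subjects notable at baseline should be balanced between arms; a common factor (1 − *q*) leaves the risk ratio unchanged in expectation. The protocol's risk summary (4.5) does not name blood pressure.

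A reader might infer more than the documents support:

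- *That a subject who enters above a limit can never register any blood-pressure event.* This is not so, because systolic and diastolic pressure are separate rows.
- *That this is the only categorical blood-pressure output.* It is not, because adverse events are also tabulated.
- *That the incidence is certainly understated.* This depends on a denominator the SAP leaves ambiguous.
- *That the subjects left out are those most likely to rise.* No passage says so, and high baseline readings tend to fall on remeasurement.

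**Conclusion.** The point holds in a narrow form. Within one parameter and direction, the notable count cannot show worsening in a subject who is already notable at baseline, and the entry criteria admit such subjects. The same SAP avoids this for lipids and liver tests. The gap also applies in principle to the low limits and to pulse, which follow the same rule.

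The conclusion rests on the plain reading of newly occurring as relative to baseline. How many subjects are affected cannot be taken from the documents. The factor of 0.70–0.95 rests on the assumed 5–30% and on keeping those subjects in the denominator. No bias between arms is shown, and no efficacy result is touched. Severity: minor.

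**What to change.** In SAP 2.8.3.1 and Table 2-4:

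1. Add a second, higher reporting tier for systolic and diastolic pressure, counted when newly reached. The protocol's own 160/95 is a natural example, used as a reporting threshold and not as a clinical rule. In the table of pairs under the check, rows 1 to 4 would then register systolic events and rows 2 to 4 diastolic events; the 2 mmHg crossing in row 5 would not. Alternatively, add a shift table by arm from baseline category to worst post-baseline category, as is done for laboratory data.
2. State that newly occurring is relative to baseline, and report the existing 140/90 tier among subjects not already notable at baseline for that parameter and direction.
3. Do not simply add worsening without a tier or a minimum change, because a rise of 1 mmHg would then count.

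The second tier has its own limits. It does not see a rise that stays below 160/95. If the entry ceiling requires both components, a few subjects could start above the new tier in one parameter; the at-risk denominator in item 2 should then apply to that tier as well.

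The cost is SAP wording, a few extra table rows and a denominator per parameter, using data already collected. SAP 2.14 says the Week 16 analysis has been done, so the change would enter with the final analysis outputs.

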2.9 Pharmacokinetic endpoints

During modeling of the PK of secukinumab, the broad principles outlined in the [FDA Guidance for Industry: Population Pharmacokinetics] will be followed.

All completed subjects with quantifiable pharmacokinetic (PK) measurements will be included in the PK data analysis. Serum concentrations will be expressed in mass per volume units. All concentrations below the limit of quantification as well as missing data will be labeled as such in the concentration data listings. PK concentrations will be summarized by visit and treatment group. In addition to mean, standard deviation (SD), coefficient of variation (CV), median and quartiles, the geometric mean and geometric coefficient of variation (CV), minimum and maximum, as well as n and n(log) will be presented. The formula for deriving the geometric mean and CV (%) is as follows:

- CV(%) = (SD/mean)*100,
- geometric mean=exp((sum of log transformed data) / number of non-missing data points after log transformation),
- geometric CV = sqrt(exp(variance of log-transformed data)-1)*100.

In addition, sample number, concentration, sample date, sample time and elapsed time from first dose (in days) will be listed by treatment sequence.

Values below lower limit of quantification/below detection limit will be imputed by 0.

Novartis	Confidential	Page 23 of 45
SAP		Study No. CAIN457P12301

Pharmacokinetic data of the study treatment will be analyzed with a populationpharmacokinetic mixed effects model. The analysis will be based on a pooled data set, including PK samples from previous studies. The modeling approach will be further detailed in a modeling plan. Results will be reported separately.

